2. INTRODUCTION

The purpose of this statistical analysis plan (SAP) is to prospectively (a priori) outline the types of analyses and presentations of the safety, efficacy, and PK data.

This document contains information to support the generation of a Clinical Study Report (CSR) for Clinical Protocol PTC124-GD-030-DMD, including detailed descriptions of the statistical methodologies to be applied, as well as the post-text tables, figures, analysis summary tables, and subject data listings intended to present the analysis results.

The structure and content of this SAP provides sufficient detail to meet the requirements identified by the FDA and International Conference on Harmonization of Technical Requirements for Registration of Pharmaceuticals for Human Use (ICH): Guidance on Statistical Principles in Clinical Trials.

3. STUDY OBJECTIVES AND ENDPOINTS

3.1. Study Objectives

The primary objective of this study is to evaluate the safety of ataluren as measured by type, frequency, severity, timing, and relationship to study drug of treatment emergent adverse events (TEAEs), laboratory abnormalities and electrocardiograms (ECGs).

There are 5 secondary objectives of the study, presented in the order from section 3.2 of the protocol:

- Evaluate the plasma pharmacokinetics (PK) of ataluren in subjects aged ≥ 2 to < 5 years old with nmDMD
- Assess proximal muscle function using timed function tests (TFTs)
- Assess change in physical function using the North Star Ambulatory Assessment (NSAA)
- Determine the effect of ataluren on weight, height, and body mass index (BMI)
- Assess the palatability of ataluren

3.2. Study Design

Protocol PTC124-GD-030-DMD is a Phase 2, multiple-dose, open-label study evaluating the safety, and pharmacokinetics (PK) of ataluren in subjects aged ≥ 2 to < 5 years old with Nonsense Mutation Dystrophinopathy (nmDMD). In nmDMD, early start of treatment is important and, therefore, it is relevant to understand the correct and tolerable dose in this age group, particularly since ataluren is dosed by weight. This study is composed of 4 periods: a 4-week screening period, a 4-week study period, and a 48-week extension period for subjects who complete the 4-week study period (52 weeks total treatment), and a 4-week post-treatment follow-up period. The objective of the 48-week extension period is to assess the long-term safety of chronic administration of ataluren in this subject population.

3.3. Schedule of Assessments

The Schedule of Assessments is presented in Table 2 of the protocol. The planned assessment times are Day -28 (Screening); Day 1 for Baseline assessment for the Ataluren Treatment Period; Day 28, 112, 196, 280, 364 (Ataluren Treatment Period), and Day 392 (Follow-up Period).

3.4. Endpoints

3.4.1. Primary Endpoints

There are 4 primary endpoints defined in the protocol for the study.

- Overall safety profile in terms of the type, frequency, severity, timing, and relationship to study therapy of any adverse events or abnormalities of physical findings, laboratory tests, or ECGs

- Occurrence of any dose-limiting toxicities (DLTs)
- Drug discontinuations due to adverse events
- Serious adverse events (SAEs)

Adverse events will be monitored throughout the course of the study and TEAEs will be reported from the time of study drug administration during the 4-week PK study period through the extension period (study day 392 / week 56). Subjects must be followed for adverse events and serious adverse events for at least 28 days after the last dose of ataluren. A subject withdrawn from the study because of an AE or SAE must be followed by the Investigator until clinical recovery is complete and laboratory results have returned to normal, or until progression has been stabilized.

The physical examinations will include the following body system or organ assessments. The results will be classified as normal or abnormal.

- Cardiovascular system
- Chest and lungs
- Thyroid
- Abdomen
- Nervous System
- Skin and mucosae
- Musculoskeletal
- Eyes, Ears, Nose, Mouth, Throat
- Spine
- Lymph Nodes
- Extremities
- Other

Abnormal laboratory tests will be reported as adverse events under the system organ class of Investigations. Hematology laboratory assessments will include white blood cell count with differential, hemoglobin, hematocrit, other red cell parameters, and platelet count. These parameters will be measured at every protocol-specified study visit. Biochemistry laboratory assessments will include sodium, potassium, chloride, bicarbonate, blood urea nitrogen, creatinine, magnesium, calcium, phosphorus, uric acid, glucose, total protein, albumin, bilirubin (total, direct, and indirect), AST, ALT, GGT, CK, lactate dehydrogenase, alkaline phosphatase, total cholesterol, high-density lipoprotein, low-density lipoprotein, triglycerides, and cystatin C. These parameters will be measured at every protocol-specified study visit. Urinalysis will include analysis for pH, specific gravity, glucose, ketones, blood, protein, urobilinogen, bilirubin, nitrite, and leukocyte esterase. These parameters will be measured at every protocol-specified study visit.

A 12-lead ECG will be obtained at screening, Week 4 (Visit 3), Week 52 (Visit 7/End of Treatment), and 4-week Follow-up (Visit 8). ECGs will be interpreted for clinical significance and classified as Normal, Abnormal, Not Clinically Significant, or Abnormal, Clinically Significant.

3.4.2. Secondary Endpoints

There are 5 secondary endpoints that cover PK, performance measurements, physical examination and palatability (ref. Section 3.4 from the protocol):

Ataluren concentrations in plasma will be analyzed to derive the pharmacokinetics using standard, non-compartmental methods. On each of the sampling days (Study Days 1 and 28), blood samples for ataluren concentration assessments will be collected immediately pre-dose and at specified time points following the morning, midday, and evening doses. The parameters to be derived are as follow:

- Area under the plasma concentration time curve from time zero to the time of last quantifiable concentration (AUC_{0-t})
- Area under the plasma concentration time curve from time zero up to 10 hours after the morning dosing (AUC_{0-10})
- Maximum observed plasma concentration (C_{max})
- Concentration at the end of the first (morning) dosage interval ($C_{trough@6h}$)
- Time of maximum observed plasma concentration (t_{max})
- The accumulation ratio for the AUC from day 1 and 28:
 $AR(AUC) = (AUC_{0-t}) \text{ on Day 28} / (AUC_{0-t}) \text{ on Day 1}$
- The accumulation ratio for the C_{max} from day 1 and 28: $AR(C_{max}) = (C_{max}) \text{ on Day 28} / (C_{max}) \text{ on Day 1}$

TFTs assessed prior to ataluren dosing on the first day of treatment (Visit 2), Week 28 (Visit 5), and Week 52 (Visit 7/ET). TFTs include:

- Time taken to run/walk 10 meters,
- Time to climb 4 stairs,
- Time to descend 4 stairs, and
- Time to stand up from a supine position.

NSAA will be performed prior to ataluren dosing on the first day of treatment (Visit 2), Week 28 (Visit 5), and Week 52 (Visit 7/ET). For each of the evaluations, the subject will be scored with a 0 (Unable to achieve independently), 1 (Modified method but achieves goal independent of physical assistance from another) or a 2 (Normal – no obvious modification of activity). The full scale is presented below.

- Stand (0, 1 or 2)
- Walk (0, 1 or 2)
- Stand up from chair (0, 1 or 2)
- Stand on one leg – right (0, 1 or 2)
- Stand on one leg – left (0, 1 or 2)
- Climb box step – right (0, 1 or 2)
- Climb box step – left (0, 1 or 2)
- Descend box step – right (0, 1 or 2)
- Descend box step – left (0, 1 or 2)

-
- Gets to sitting (0, 1 or 2)
 - Rise from floor (0, 1 or 2)
 - Lifts head (0, 1 or 2)
 - Stands on heel (0, 1 or 2)
 - Jump (0, 1 or 2)
 - Hop right leg (0, 1 or 2)
 - Hop left leg (0, 1 or 2)
 - Run (10m) (0, 1 or 2)

The total of the previous 17 items will be summed on an intra-subject basis to obtain the total score. The best total score is 34 and the worst is 0.

Recent updates to the NSAA have removed ‘Lifts Head’ from the total score. Although the results from all 17 items have been collected, a summary will be presented based on the 16 items without the result from ‘Lifts Head’. The results of these 16 items will be summed on an intra-subject basis to obtain the total score. The best total score is 32 and the worst is 0.

Two additional subset summaries will be generated from the 17 items in the NSAA. The first is an 8-item NSAA subscale. This 8-item subscale will include the following 8 items from the full NSAA.

- Stand (0, 1 or 2)
- Walk (0, 1 or 2)
- Stand up from chair (0, 1 or 2)
- Climb box step – right (0, 1 or 2)
- Climb box step – left (0, 1 or 2)
- Gets to sitting (0, 1 or 2)
- Jump (0, 1 or 2)
- Run (10m) (0, 1 or 2)

The total of these 8 items will be summed on an intra-subject basis to obtain the total score for the 8-item subscale. The best total score is 16 and the worst is 0.

The second is a 3-item NSAA subscale. This 3-item subscale will include the following 3 items from the full NSAA.

- Stand (0, 1 or 2)
- Walk (0, 1 or 2)
- Stand up from chair (0, 1 or 2)

The total of these 3 items will be summed on an intra-subject basis to obtain the total score for the 3-item subscale. The best total score is 6 and the worst is 0.

Two additional measures will also be recorded and summarized.

- Rise from Floor Time (seconds)
- Run (10m) Time (seconds)

Ataluren palatability characteristics will be based on the parent/caregiver questionnaire. The first question below will be asked of the subject and the response from the subjects will be recorded as *bad, not sure, or good*. The second and third questions will be asked of the caregiver and the response from the caregiver will be recorded as *strongly disagree, disagree, neither agree nor disagree, agree, or strongly agree*. The specific questions are presented below.

- *How did the medicine taste?*
- *On the basis of reaction/facial expression of your child, do you think that the medication is pleasant?*
- *You sometimes have problems in giving the medication to your child because he/she refuses to take it or throws it up.*

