3.4. Secondary Endpoints

The secondary endpoints are:

- Pharmacokinetic parameters (t_{max} , $t_{1/2}$, C_{max} , $C_{trough@6h}$, AUC_{0-10}), CL/F, and V_c/F based on frequent blood sampling for PK on Days 1 and 28 of ataluren treatment. On each of these days, blood samples for ataluren concentration assessments will be collected immediately pre-dose and at specified time points following the morning, midday, and evening doses. Ataluren concentrations in plasma will be analyzed using a validated HPLC-MS/MS method.
- TFTs (time to walk/run 10 meters, time to climb 4 stairs, time to descend 4 stairs, and time to stand up from a supine position)
- NSAA
- Changes in body weight, height, and BMI
- Ataluren palatability characteristics as determined by a parent/caregiver questionnaire

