8.2.5. Height, Weight and Physical Examination

Height (in cm) and weight (in kg) will be measured at all study visits. A full physical

examination (including evaluation of the cardiovascular system, chest and lungs, thyroid, abdomen, nervous system, skin and mucosae, musculoskeletal system, eyes, ears, nose, mouth, throat, spine, lymph nodes, and extremities) will be conducted at Screening (Visit 1) and 4-week Follow-up (Visit 8), 4 weeks after discontinuation of study drug.

Physical examinations may also be performed at any time during the study as clinically indicated.

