11.3. General Statistical Considerations

By-subject listings will be created for each eCRF module. Summary tables for continuous variables will contain the following statistics: N, mean, median, standard deviation, standard error, minimum, maximum, and 95% confidence intervals (CIs) as appropriate. Summary tables for categorical variables will include N and percentage. Graphical techniques will be used when such methods are appropriate and informative.

Transformations of the data may be explored if warranted by the distribution of the data.

All analyses will be performed using Statistical Analysis System (SAS® Version 9.0 or higher).

The primary analysis will be conducted on data obtained during the 4-week PK period of the study and may be reported separately from the extension study data.

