11.7.3. Vital Signs and ECGs

Vital signs (height, weight, BMI, pulse rate, and body temperature) and ECGs will be listed and summarized by visit. Where appropriate, changes from baseline will be presented by visit.

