8. DEMOGRAPHICS AND OTHER BASELINE CHARACTERISTICS

8.1. Baseline Demographic Factors and Medical History

All subjects in the Safety Population will be included in summary of demographic information in Table 14.1.3 entitled *Demographics and Baseline Characteristics* (Safety Population). This table summarizes the subject population with respect to gender, age (years) at screening, race and ethnicity. Age will be reported in months and years and summarized with descriptive statistics: n, arithmetic mean, SD, median, range (*i.e.*, minimum and maximum values). The number and percent of each gender, race, and ethnicity category will be presented using counts and percentages. Race will be presented using the following categories:

- Caucasian or White
- Black or African American
- Asian
- American Indian or Alaska Native
- Native Hawaiian or other Pacific Islander
- Other

The supportive data for Table 14.1.3 are presented in Listing 16.2.4.1 entitled *Demographics and Subject Characteristics* (Safety Population). This listing will be sorted by subject number.

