10. EFFICACY

Observed values and changes from baseline in timed function tests and NSAA total score will be summarized using descriptive statistics for the evaluable population.

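### Change in weight, height and BMI is one of five secondary endpoints, but the SAP describes only four and gives this one no analysis, table or listing

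*SAP*

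**What the plan says.** The protocol treats growth as an endpoint from objective to analysis. Protocol 3.2 makes the effect of ataluren on weight, height and BMI a secondary objective, and Protocol 3.4 lists the matching endpoint: "Changes in body weight, height, and BMI". Protocol 8.2.5 provides the data: "Height (in cm) and weight (in kg) will be measured at all study visits". The schedule of events marks both at Visits 1 to 8, and SAP 16 keeps both rows. Protocol 11.7.3 gives the analysis: "Vital signs (height, weight, BMI, pulse rate, and body temperature) and ECGs will be listed and summarized by visit". It adds change from baseline by visit where appropriate.

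The SAP keeps the objective in section 3.1. Section 3.4.2 cites Protocol 3.4 and announces the same number of endpoints: "There are 5 secondary endpoints that cover PK, performance measurements, physical examination and palatability". The text that follows covers pharmacokinetics, timed function tests, the North Star assessment (NSAA) and palatability, and then stops.

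**The concern.** A declared secondary endpoint is measured at every visit, yet the document that sets out the study report's tables and listings has no place for it. A programmer working from the SAP alone would not derive BMI, would not summarise height or weight, and would not notice that anything was missing, because the announced total of five looks complete.

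There is also a question of method. The objective is worded as an effect of the drug. The study has one arm, and its boys are followed for about a year at an age when height and weight rise anyway. A by-visit table of raw change alone would show mostly growth, and a reader could not tell from it whether growth was faster, slower or unchanged on treatment.

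**Working it through.** No formula or error rate is involved in the main point. The check is a count, followed by a search of the places where the endpoint could sit.

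**Step 1: the SAP's own figure of five.** Protocol 3.4 lists five endpoints, so the announced total matches its source. The SAP's descriptions do not reach that total:

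| Protocol 3.4 endpoint | Described in SAP 3.4.2 | SAP analysis section | Main SAP 14 outputs |
|---|---|---|---|
| Pharmacokinetics | yes | 11.1, 11.2 | Tables 14.2.4, 14.2.5 |
| Timed function tests | yes | 10.1 | Table 14.2.1 |
| NSAA | yes | 10.2 | Tables 14.2.2.1 to 14.2.2.2 |
| Weight, height, BMI | no | none | none |
| Palatability | yes | 10.3 | Table 14.2.3 |

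Announced 5, described 4, missing 5 − 4 = 1. Counting the two NSAA times (rise from floor and 10 m run) as a fifth endpoint does not rescue the total. They are presented as part of the NSAA, and they are not the item in Protocol 3.4.

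**Step 2: where else growth could be.**
- SAP 8.1 summarises baseline "with respect to gender, age (years) at screening, race and ethnicity. Age will be reported in months and years". It includes no baseline weight or height.
- SAP 10 opens with "Observed values and changes from baseline in timed function tests and NSAA total score will be summarized" and goes on to palatability. Growth is not mentioned.
- SAP 12.3 is the counterpart of Protocol 11.7.3. It names five parameters, and none is height, weight or BMI.
- SAP 12.5 counts abnormal findings in 12 body systems. That cannot give a change in kg, cm or BMI.
- SAP 14 has no table, figure or listing that names these measures.
- SAP 4 defines the Evaluable Population by timed function tests, NSAA or palatability, so no population is assigned to growth.

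Elsewhere in the SAP, weight appears as the basis for dosing (3.2, 3.6), and height and weight appear as schedule rows (16).

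**Step 3: is the omission explained?** It is not. When SAP 11.2 leaves out two pharmacokinetic parameters that the protocol calls for, it names them and gives the reason. Nothing comparable is said about growth.

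**Step 4: how much ageing raw change contains.** Day 1 to Day 364 is 363 days: 363/365.25 = 0.99 years. For a boy aged 2 at entry that is 0.99/2 ≈ 50% of his age; for one just under 5 it is 0.99/5 ≈ 20%. The documents give no growth rates, so the expected gain in cm or kg cannot be stated from them. BMI is a ratio built from two growing quantities, so the direction of its change cannot be assumed either.

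**Step 5: the age range a growth reference must cover.** The youngest age is 2. The oldest, if the age limit is checked at screening on Day −28, is below 5 + (28 + 391)/365.25 = 5 + 1.15 = 6.15 years at Day 392, or about 6.2 when rounded up.

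**Step 6: is there another comparator?** The natural-history extract in SAP 3.9 takes demographics at study entry, timed function tests and NSAA. Follow-up height and weight are not among the data listed, so it offers no growth control.

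**The case against.** The strongest reply is that the analysis already exists. Protocol 11.7.3 plans the listing, the by-visit summary and change from baseline. Protocol 11.3 adds "By-subject listings will be created for each eCRF module", and SAP 5 defines summary statistics, baseline and change for all presentations. SAP 3.4.2 also names physical examination among its categories, and Protocol 8.2.5 groups height and weight with that examination. All this suggests a drafting slip.

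Much of that stands. A reader might infer that the endpoint was abandoned, or that any growth summary would be improvised after the fact. The documents support neither inference: the protocol's plan remains in force, and the SAP keeps the objective and counts the endpoint. What the reply does not supply is the link. The SAP's general conventions name no variable, population, BMI derivation or output for growth. SAP 12.3, where the protocol's plan should have been carried over, is a list without these measures.

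A reader might also infer that the trial is set to claim a drug effect from a rise in raw height or weight. It is not. No test of growth against zero is planned, and SAP 5 describes the study as primarily descriptive, with probability values only as an informational option. The weakness of raw change is one of interpretation; no error rate is at issue.

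Finally, it can be said that z-scores go beyond the endpoint as worded and still would not isolate a drug effect. Both statements are true. Z-scores do, however, remove the largest known source of change at small cost, and raw change can be shown beside them.

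**Conclusion.** The point holds as an omission from the SAP. One of five secondary endpoints has no SAP description, analysis, population, table or listing, although its data are collected at 8 of 8 visits and the protocol plans a summary. No reason is given. Raw change, even if reported as the protocol plans, cannot on its own answer an objective worded as an effect of the drug, because normal growth is mixed into it.

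The severity is minor to should-fix. The endpoint is secondary and descriptive, the primary safety analysis is untouched, and neither sample size nor data collection is affected. The gap can be closed without loss.

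The conclusion rests on the text of the two documents. The eCRF and study manual are not available, so it is unknown whether BMI is calculated there or whether height and weight would appear in an existing by-subject listing. Neither would provide the missing summary of change. The age calculation assumes that the upper age limit is applied at screening and that visits fall on their scheduled days.

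**What to change.** Carry Protocol 11.7.3 into SAP 3.4.2, 12.3 and 14:

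- Describe the fifth endpoint in SAP 3.4.2.
- Add one by-visit table and one by-subject listing of weight, height and BMI in the Safety Population, using the SAP 5 definitions of baseline and change.
- Derive BMI as weight in kg divided by the square of height in metres.
- Show observed values, age- and sex-standardised z-scores, and change from baseline in both. Name one growth reference in advance, covering age 2 to about 6.2 years.
- State that, without a control arm, z-scores account for normal growth but do not separate a drug effect from the effects of the disease or of corticosteroids.

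The cost is one table, one listing, and the choice and programming of a growth reference. Age in months is already planned in SAP 8.1, and visit dates supply the rest. No visit, measurement or blood sample is added.

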3.5. Sample Size Justification

The planned sample size of 12 subjects for this study should provide adequate precision for the prediction of PK parameters (apparent clearance and volume of distribution).

3.6. Study Treatments and Dose Administration

Dosing of ataluren is based on milligrams of drug per kilogram of subject body weight; body weight is re-assessed every 12 weeks. All subjects will receive approximately 10, 10, 20 mg/kg ataluren 3 times daily (TID) for 4 weeks during the PK portion and for 48 weeks during the extension period. Three doses will be administered each day; the first dose will be in the morning, the second dose will be administered in the middle of the day (midday), and the third dose will be administered in the evening.

3.7. Estimated Duration of Subject Participation and Follow-up

Subjects who do not terminate early from the study will be followed for 56 weeks; a total of 52 weeks after the initial administration of the study drug. If a subject completes the study with an ongoing AE, the site will continue to follow up with the subject until resolution if ≤ 28 days from the last dose of study drug. If, after 28 days the AE is still continuing but not assessed as serious, the outcome will be recorded as ongoing and no further follow up will be necessary. If a subject completes the study with an ongoing SAE, the subject will be followed until resolution or stabilization or until no further information can be obtained.

